9.1.6 Physical examinations

Normal and clinically significant and non-clinically significant abnormal findings will be specified and summarised by treatment and cohort, and by assessment time point. Changes over time will be presented using shift tables, if appropriate. Physical examination data for eligibility (screening) in Part B will only be listed.

9.1.7 Cream absorption (Part B)

Cream absorption measured on a 4-point scale will be presented using a frequency table by cohort. The time until adequate abruption, measured at 30 min, 1h, and 2 h, will be presented by cohort in the same frequency table. Adequate abruption will be interpreted as equivalent to a cream absorption score of at least “3 = Mostly absorbed” on the 4-point cream absorption scale.

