11.3.7 Cream absorption evaluation (Part B)

The cream absorption will be documented by photography of the administered area at timepoints specified in Table 8.1-4.

In addition, the cream absorption will be assessed at 30 minutes, 1 hour, and 2 hours post-administration on a 4-point scale scale:

“1= not absorbed”; “2= somewhat absorbed”; “3= mostly absorbed”; “4= completely absorbed”

The time until adequate absorption will be measured up to 2 hours after administration.

The Sponsor and the Investigator will determine if more cohorts will be explored at a higher or lower dose in order to reach the optimal dose/area or if the absorption is sufficient.

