5 STATISTICAL AND ANALYTICAL PLANS

5.1 Sample size calculation and number of participants

No formal sample size calculation has been performed for this trial. The proposed sample size is considered sufficient to provide adequate information to meet the trial objectives.

Part A: Approximately 64 participants were planned to be screened to achieve 32 randomised participants (8 in each cohort).

Part B: Approximately 18 potential participants were planned to be screened to achieve up to 9 included participants, 3 subjects per cohort.

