5.6 Handling of dropouts, missing data and outliers

Outliers will be included in summary tables and listings and will not be handled separately in any analyses. All collected data, even if not tabulated, will be listed. Generally, no imputation of data will be performed. However, when calculating statistics for PK plasma concentrations, concentrations under LLOQ will be replaced with LLOQ/2 if more than 50% of the values for a given time point are above LLOQ. Otherwise, no statistics will be calculated for that time point. For figures presenting individual PK concentrations, no imputation is performed for values under LLOQ. For imputation of PK plasma concentration below LLOQ with the purpose of calculating PK parameters, see Section 9.2.1.

Safety laboratory concentrations under LLOQ will be replaced with LLOQ/2 and concentrations over ULOQ will be replaced with ULOQ for the purpose of calculating descriptive statistics.

In case of missing start and stop times of AEs that cannot be investigated further, missing data will be imputed according to a worst-case scenario, i.e., start time will be imputed as the closest time point post first intake of IMP and end time as 23:59, resulting in the longest possible treatment emergent duration of the AE.

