Any Blistering	xx (xx%)	xx	xx (xx%)	xx	xx	xx (xx%)
Maximum grade Blistering						
None	xx (xx%)		xx (xx%)	xx (xx%)	xx	xx (xx%)
Mild	xx (xx%)		xx (xx%)	xx (xx%)	xx	xx (xx%)
Moderate	xx (xx%)		xx (xx%)	xx (xx%)	xx	xx (xx%)
Severe	xx (xx%)		xx (xx%)	xx (xx%)	xx	xx (xx%)
Any Urticaria	xx (xx%)	xx	xx (xx%)	xx	xx	xx (xx%)
Maximum grade Urticaria						
None	xx (xx%)		xx (xx%)	xx (xx%)	xx	xx (xx%)
Mild	xx (xx%)		xx (xx%)	xx (xx%)	xx	xx (xx%)
Moderate	xx (xx%)		xx (xx%)	xx (xx%)	xx	xx (xx%)
Severe	xx (xx%)		xx (xx%)	xx (xx%)	xx	xx (xx%)
Any Discolouration	xx (xx%)	xx	xx (xx%)	xx	xx	xx (xx%)
Maximum grade Discolouration						
None	xx (xx%)		xx (xx%)	xx (xx%)	xx	xx (xx%)
Mild	xx (xx%)		xx (xx%)	xx (xx%)	xx	xx (xx%)

							m	
Moderate		xx (xx%)		xx (xx%)		xx (xx%)	xx	xx (xx%)
Severe		xx (xx%)		xx (xx%)		xx (xx%)	xx	xx (xx%)
Any Dryness		xx (xx%)	xx	xx (xx%)	xx	xx (xx%)	xx	xx (xx%)
Maximum grade Dryness								
None		xx (xx%)		xx (xx%)		xx (xx%)	xx	xx (xx%)
Mild		xx (xx%)		xx (xx%)		xx (xx%)	xx	xx (xx%)
Moderate		xx (xx%)		xx (xx%)		xx (xx%)	xx	xx (xx%)
Severe		xx (xx%)		xx (xx%)		xx (xx%)	xx	xx (xx%)

Data based on [ANALYSIS SET]. BSA: Body surface area. N: number of participants in the treatment group. Percentages are based on N. n: number of participants. m: number of events. SAS program: [PROGRAM NAME].sas.

Dataset version: ADXX YYYY-MM-DDTHH:MM:SS. Run by: [USERNAME] YYYY-MM-DDTHH:MM:SS. EDC data extracted: YYYY-MM-DDTHH:MM:SS.

Table LT 3 Local tolerability intensity grades – Part

| [PARAMETER 1] | [Assessment timepoint 1] | [RESULT 1] | xx/XX (xx%) |
|---------------|--------------------------|------------|-------------|-------------|-------------|-------------|-------------|-------------|
| | | [RESULT 2] | xx/XX (xx%) |
| | | [RESULT 3] | xx/XX (xx%) |
| | [Assessment timepoint 2] | [RESULT 1] | xx/XX (xx%) |
| | | [RESULT 2] | xx/XX (xx%) |
| | | [RESULT 3] | xx/XX (xx%) |

Data based on [population]. SAS program: [PROGRAM NAME].sas. BSA: Body surface area. N: Number of participants in the treatment group. Percentages are based on the number of observations.

Dataset version: ADXX YYYY-MM-DDTHH:MM:SS. Run by: [USERNAME] YYYY-MM-DDTHH:MM:SS. EDC data extracted: YYYY-MM-DDTHH:MM:SS.

Table LT 4 Local tolerability intensity grades – Part B (Full analysis set)

Assessment	Assessment timepoint						
[PARAMETER 1]	[Assessment timepoint 1]	[RESULT 1]	xx/XX (xx%)				
		[RESULT 2]	xx/XX (xx%)				
		[RESULT 3]	xx/XX (xx%)				

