10.2.2.5 Safety laboratory (Part A)

Table LB 1 Safety laboratory measurements: Clinical chemistry – Part A (Full analysis set)

Assessment (unit)	Result category	Assessment timepoint	[REDACTED]				
[PARAMETER 1] (unit)	Measured value	[Assessment timepoint 1]	n	xx/xx/xx	xx/xx/xx	xx/xx/xx	xx/xx/xx
			n/BLQ/ULQ	x.xx (x.xx)	x.xx (x.xx)	x.xx (x.xx)	x.xx (x.xx)
			Mean (SD)	x.xx (x.xx)	x.xx (x.xx)	x.xx (x.xx)	x.xx (x.xx)
	[Assessment timepoint 2]		Median (Min, Max)	x.xx (x.x, x.x)	x.xx (x.x, x.x)	x.xx (x.x, x.x)	x.xx (x.x, x.x)
		n	xx	xx	xx	xx	xx
			n/BLQ/ULQ	xx/xx/xx	xx/xx/xx	xx/xx/xx	xx/xx/xx
			Mean (SD)	x.xx (x.xx)	x.xx (x.xx)	x.xx (x.xx)	x.xx (x.xx)
			Median (Min, Max)	x.xx (x.x, x.x)	x.xx (x.x, x.x)	x.xx (x.x, x.x)	x.xx (x.x, x.x)

Assessment (unit)	Result category	Assessment timepoint	[Redacted]				
Change from baseline	[Assessment timepoint 1]	n	xx	xx	xx	xx	xx
		n/BLQ/ULQ	xx/xx/xx	xx/xx/xx	xx/xx/xx	xx/xx/xx	xx/xx/xx
		Mean (SD)	x.xx (x.xx)				
	[Assessment timepoint 2]	Median (Min, Max)	x.xx (x.x, x.x)				
		n	xx	xx	xx	xx	xx
		n/BLQ/ULQ	xx/xx/xx	xx/xx/xx	xx/xx/xx	xx/xx/xx	xx/xx/xx
Relative change from baseline (%)	[Assessment timepoint 1]	Mean (SD)	x.xx (x.xx)				
		Median (Min, Max)	x.xx (x.x, x.x)				
		n	xx	xx	xx	xx	xx
	[Assessment timepoint 2]	n/BLQ/ULQ	xx/xx/xx	xx/xx/xx	xx/xx/xx	xx/xx/xx	xx/xx/xx
		Mean (SD)	x.xx (x.xx)				
		Median (Min, Max)	x.xx (x.x, x.x)				

Data based on [population]. BSA: Body surface area. n: Number of observations. SD: Standard deviation. CV%: Coefficient of variation described as percentage. IQR: Inter-quartile range. Q1: Lower quartile. Q3: Upper quartile. NC: Not calculated - number of evaluable observations less than 3. NA: Not available - no evaluable observations. SAS program: [PROGRAM NAME].sas.

Dataset version: ADXX YYYY-MM-DDTHH:MM:SS. Run by: [USERNAME] YYYY-MM-DDTHH:MM:SS. EDC data extracted: YYYY-MM-DDTHH:MM:SS.

Table LB 2 Safety laboratory interpretations: Clinical chemistry – Part A (Full analysis set)

Assessment	Assessment timepoint	[Redacted]					
[PARAMETER 1]	[Assessment timepoint 1]	[RESULT 1]	xx/XX (xx%)				
		[RESULT 2]	xx/XX (xx%)				
		[RESULT 3]	xx/XX (xx%)				
	[Assessment timepoint 2]	[RESULT 1]	xx/XX (xx%)				
		[RESULT 2]	xx/XX (xx%)				
		[RESULT 3]	xx/XX (xx%)				

Data based on [population]. SAS program: [PROGRAM NAME].sas. BSA: Body surface area.

Dataset version: ADXX YYYY-MM-DDTHH:MM:SS. Run by: [USERNAME] YYYY-MM-DDTHH:MM:SS. EDC data extracted: YYYY-MM-DDTHH:MM:SS.

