10.2.2.7 Cream absorption (Part B)

Table QS 1 Cream absorption – Part B (Full analysis set)

[Redacted]					
Assessment (unit)	Assessment timepoint				
Cream absorption	[Assessment timepoint 1]	1= Not absorbed	xx/XX (xx%)	xx/XX (xx%)	xx/XX (xx%)
		2= Somewhat absorbed	xx/XX (xx%)	xx/XX (xx%)	xx/XX (xx%)
		3= Mostly absorbed	xx/XX (xx%)	xx/XX (xx%)	xx/XX (xx%)
		4= Completely absorbed	xx/XX (xx%)	xx/XX (xx%)	xx/XX (xx%)
	[Assessment timepoint 2]	1= Not absorbed	xx/XX (xx%)	xx/XX (xx%)	xx/XX (xx%)
		2= Somewhat absorbed	xx/XX (xx%)	xx/XX (xx%)	xx/XX (xx%)
		3= Mostly absorbed	xx/XX (xx%)	xx/XX (xx%)	xx/XX (xx%)
		4= Completely absorbed	xx/XX (xx%)	xx/XX (xx%)	xx/XX (xx%)
Time until adequate abruption (unit)	[Assessment timepoint 1]	30 min	xx/XX (xx%)	xx/XX (xx%)	xx/XX (xx%)
		1 h	xx/XX (xx%)	xx/XX (xx%)	xx/XX (xx%)
		2 h	xx/XX (xx%)	xx/XX (xx%)	xx/XX (xx%)
	[Assessment timepoint 2]	30 min	xx/XX (xx%)	xx/XX (xx%)	xx/XX (xx%)
		1 h	xx/XX (xx%)	xx/XX (xx%)	xx/XX (xx%)
		2 h	xx/XX (xx%)	xx/XX (xx%)	xx/XX (xx%)

Data based on [population]. SAS program: [PROGRAM NAME].sas. Adequate abruption is interpreted as equivalent to a cream absorption score of at least "3 = Mostly absorbed" on the 4-point cream absorption scale. BSA: Body surface area N: Number of participants in the treatment group. n: Number of observations.

Dataset version: ADXX YYYY-MM-DDTHH:MM:SS. Run by: [USERNAME] YYYY-MM-DDTHH:MM:SS. EDC data extracted: YYYY-MM-DDTHH:MM:SS.

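### Does the Part B summary of time to adequate cream absorption lose participants who are still below the threshold at 2 hours?

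*SAP*

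**What the plan says.** Protocol 11.3.7 sets a 4-point score, assessed at 30 minutes, 1 hour and 2 hours, and adds: "The time until adequate absorption will be measured up to 2 hours after administration". Two of the four levels (1 and 2) lie below adequate. Protocol 17.6.7 asks for the scores in a frequency table and for the time to be summarised, both by cohort.

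SAP 9.1.7 fixes adequate as a score of at least 3 and says: "The time until adequate abruption, measured at 30 min, 1h, and 2 h, will be presented by cohort in the same frequency table". The odd noun is a slip for absorption, carried over from Protocol 17.6.7; the SAP's own definition makes the meaning clear.

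Table QS 1 (SAP 10.2.2.7) is titled for the full analysis set. It has four score rows per assessment time, and time rows for 30 min, 1 h and 2 h, each shown as a count over a denominator with a percentage. Its footnote includes "N: Number of participants in the treatment group. n: Number of observations" but does not say which of the two the denominator is. The column header is blacked out.

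SAP 5.6 says "Generally, no imputation of data will be performed" and that all collected data will be listed. SAP 5.1 plans "up to 9 included participants, 3 subjects per cohort". SAP 10.4 provides Listing 16.2.5-5, the individual cream absorption evaluations.

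**The concern.** A time-to-threshold variable observed for only 2 hours needs a place for those who do not reach the threshold. The design expects that this can happen, because optional cohorts at other amounts may be added depending on how well the cream absorbs. Yet the time rows stop at 2 h, so a participant scored 1 or 2 throughout seems to have no category, and SAP 5.6 has no rule for the case.

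The denominator also looks open. Some sister tables settle theirs: the footnote to Table LT 3 says "Percentages are based on the number of observations". Table LB 2 does not; its footnote starts "Data based on [population]. SAS program: [PROGRAM NAME].sas. BSA: Body surface area" and gives no percentage base. Table QS 1 also repeats the time rows under each assessment time, although a time to first adequate score is one value per participant.

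At stake would be the consistency of the summary table for Part B's only endpoint: two programmers could print different percentages from the same data, and the time rows might not agree with the score rows beside them.

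**Working it through.** The documents give no figure to reproduce, so the check is whether any permitted reading hides a participant who did not reach the threshold.

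**Inputs.** Cohort size 3 (SAP 5.1); scoring at 30 min, 1 h and 2 h (Protocol 11.3.7); adequate means a score of at least 3 (SAP 9.1.7). Data are taken as complete, and no score falls back once it has reached 3.

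**General case.** Let k be the number who reach 3 by 2 h. If the rows give first attainment, they add to k/3 with the cohort as base, or k/k with only those who reached as base.

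| k | Base = cohort | Base = those who reached | Difference | 2 h score rows at 1 or 2: (3 − k)/3 |
|---|---|---|---|---|
| 0 | 0/3 (0%) | empty | – | 3/3 |
| 1 | 1/3 (33%) | 1/1 (100%) | 100 − 33 = 67 points | 2/3 |
| 2 | 2/3 (67%) | 2/2 (100%) | 100 − 67 = 33 points | 1/3 |
| 3 | 3/3 (100%) | 3/3 (100%) | 0 | 0/3 |

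The last column does not depend on how the time rows are read, and it counts every participant below the threshold.

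**Worked cohort (hypothetical).** Scores at 30 min, 1 h and 2 h: first participant 2, 3, 4; second 2, 3, 3; third 1, 2, 2.

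| Reading of the time rows | 30 min | 1 h | 2 h | Where the third participant is |
|---|---|---|---|---|
| First attainment, base = cohort | 0/3 | 2/3 (67%) | 0/3 | no time row; rows add to 2/3 |
| First attainment, base = those who reached | 0/2 | 2/2 (100%) | 0/2 | no time row; the base of 2 is printed |
| Adequate by each time | 0/3 | 2/3 (67%) | 2/3 (67%) | complement of the 2 h row, 1/3 |

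The 2 h score rows read 1/3 at score 4, 1/3 at score 3, 1/3 at score 2 and 0/3 at score 1. All three readings stand beside that visible 1/3 (33%) below adequate. The third reading agrees with the score rows exactly and needs no extra category. The SAP wording allows it.

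**The denominator.** With complete data each participant contributes one score at each time, so observations and cohort size are both 3. To get k/k, a participant with three recorded scores must count as having no observation. That is a strained use of the term.

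**How often it could arise.** The documents give no rate of non-attainment. For an assumed probability q per participant, the chance of at least one is 1 − (1 − q)^3 in a cohort and 1 − (1 − q)^9 in nine participants. For q = 0.1, 0.2, 0.3 and 0.5 this is 27%, 49%, 66% and 88% in a cohort, and 61%, 87%, 96% and 99.8% in nine. The situation may well occur, so the point cannot be dismissed as unlikely; it rests on what the table shows when it does.

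**Use of the table.** Under Protocol 11.3.7 the Sponsor and the Investigator decide during Part B whether to explore another amount. Under Protocol 16.7 analysis follows database lock. Table QS 1 therefore does not drive that decision.

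**The case for a change.** The best case for a change is that this is the summary of Part B's only endpoint, that failure to absorb within 2 hours is one of the results the part exists to find, and that a SAP should settle categories and denominators before a programmer has seen open-label data. The 30 min, 1 h and 2 h labels are literal text in both SAP 9.1.7 and the shell, so they cannot be waved away as placeholders. One added row and a footnote would cost almost nothing.

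Part of this stands. The visible text does not say whether the rows are first attainment or cumulative, and on the first-attainment reading a non-reacher has no time row. The claim that the denominator is undefined is weaker. The column header is blacked out, headers that survive elsewhere (such as Table CM 1) carry the group size, and the table title already names the full analysis set. The nesting under assessment times is visibly template text: the shell shows two generic times where three are scored.

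What does not stand is the consequence. The time rows are not bound to be incomplete or in conflict with the score rows, because the cumulative reading is neither. Even on the least favourable reading, the printed base differs from the cohort size and the score rows beside it show why.

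**Conclusion.** No change is called for. The plan leaves a presentation detail open, and the choice affects how three rows of one descriptive table look: by at most 67 percentage points at k = 1 and 33 at k = 2, and only with a base restricted to those who reached the threshold. It does not affect what a reader can learn. With 3 participants per cohort, the 2 h score rows count everyone below adequate, and Listing 16.2.5-5 shows each person's scores. There is no test, interval or decision rule attached to the time rows.

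This rests on complete score data and on no score falling back after reaching 3. If a score is missing or reverses, the time rows and the 2 h score rows may differ for that participant, and the listing resolves it case by case. A programmer producing the table would meet the empty category at once and could show or footnote it without altering any Part B conclusion.

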9.2 Analysis of secondary endpoints

9.2.1 Pharmacokinetic analysis (Part A)

The following non-compartmental plasma PK parameters will be determined/calculated (if data permits) during the trial conduct:

- T_{max} – Time to reach C_{max}
- C_{max} – The maximum observed plasma concentration
- $AUC_{0\text{-last}}$ – Area under the plasma concentration versus time curve (AUC) from timepoint 0 to t , where t represents the timepoint of the last detectable plasma concentration
- $AUC_{0\text{-inf}}$ – AUC from timepoint 0 extrapolated to infinity
- $T_{1/2}$ – Terminal plasma elimination half-life

Parameters that are only presented in listings

- λ_{daz} – Eliminate rate constant associated with the terminal phase
- λ_{daz} lower – Lower limit on time for values to be included in the calculation of λ_{daz}
- λ_{daz} upper – Upper limit on time for values to be included in the calculation of λ_{daz}
- No points λ_{daz} – Number of points used in computing λ_{daz}
- Span – The ratio between the interval used for determination of λ_{daz} and the terminal $T_{1/2}$
- $Rsq\ adj$ – Goodness of fit statistic for the terminal phase, adjusted for the number of points used in the estimation of λ_{daz} .
- $AUC_{\text{extr}\%}$ – Percentage of $AUC_{0\text{-inf}}$ due to extrapolation from T_{last} to infinity
- T_{last} – Last observed concentration

Following units will be used:

- Time: h

- Concentration: nmol/L
- AUCs: h* nmol/L
- Lambda_z: /h

Non-compartmental analysis will be based on the actual sampling times recorded during the trial.. For the purpose of calculating PK parameters, concentrations below lower limit of quantification (LLOQ) occurring before C_{max} will be treated as zero. Concentrations below LLOQ occurring after C_{max} will be omitted from the analysis.

T_{max}, T_{last} and C_{max} will be based on the observed plasma concentration data.

All AUC will be assessed by integration of the plasma concentration vs time curve using linear interpolation for increasing plasma levels and logarithmic interpolation for decreasing plasma levels (Linear Up-Log Down method).

AUC_{0-last} will be calculated from time 0 to the time t of the last detectable plasma concentration.

For AUC_{0-inf} the area will be calculated to the last timepoint showing a measurable plasma concentration and then extrapolated to infinity using the concentration in the last quantifiable sample and lambda_z.

$$AUC_{0-inf} = AUC_{0-last} + \frac{C_{last}}{\lambda_z}$$

Formulas for calculation of AUC

- Linear trapezoidal rule:

$$AUC|_{t1}^{t2} = \delta t \times \frac{C_1 + C_2}{2}$$

- Logarithmic trapezoidal rule:

$$AUC|_{t1}^{t2} = \delta t \times \frac{C_2 - C_1}{\ln(C_2) - \ln(C_1)}$$

where t = time, c = concentration, $\delta t = t_2 - t_1$.

Formulas for interpolation (to find C* at time t* for t1 < t* < t2)

- Linear interpolation rule:

$$C^* = C_1 + \left| \frac{t^* - t_1}{t_2 - t_1} \right| (C_2 - C_1)$$

- Logarithmic interpolation rule:

$$C^* = \exp \left(\ln(C_1) + \left| \frac{t^* - t_1}{t_2 - t_1} \right| * (\ln(C_2) - \ln(C_1)) \right)$$

where t = time, c = concentration

Lambda_z, the first order rate constant associated with the terminal portion of the curve will be determined by lin-logarithmic regression of the terminal elimination phase of individual plasma concentration vs time curves. Determination of lambda_z requires identification of a sufficiently linear terminal phase (as determined by visual inspection of the lin-log plasma concentration vs time plot with the regression line) consisting of at least 3 terminal concentration values (not including C_{max}). If this is not achieved, lambda_z and its dependent PK parameters will not be reported for that profile.

In the following cases, lambda_z dependent PK parameters will be flagged in listings as potentially unreliable:

- Lambda_z estimation is based on a period of less than 1.5 times the resulting T_{1/2}.
- The Rsq adjusted value of the regression line is < 0.85.
- The estimated % extrapolated AUC is > 20% ((AUC_{0-inf}-AUC_{0-last} / AUC_{0-inf})*100).

T_{1/2} will be calculated accordingly:

$$T_{1/2} = \frac{\ln (2)}{\lambda_z}$$

Span will be calculated accordingly:

$$Span = \frac{\lambda_z \text{ upper} - \lambda_z \text{ lower}}{T_{1/2}}$$

If there is a confirmed dosing error during the trial, the pharmacokinetic data for that period will only be included in the listings but excluded from descriptive and statistical analyses. In case of missed blood samples, potential impact on PK parameters will be assessed for each individual case. PK parameters with a high degree of uncertainty due to missing samples (e.g., multiple samples missing around C_{max}) will be flagged as unreliable in the report and may in rare cases be excluded from summary tables, descriptive statistics, and statistical analysis.

9.3 Description of trial population

9.3.1 Disposition

A participant disposition will be presented by part, showing the number of screened participants; the number of withdrawn participants prior to dose, including the reason for withdrawal; the number of included participants in each cohort; the number of withdrawn participants, including the reason for withdrawal; the number of completed participants; the number of participants included in the analysis sets, and the number of participants at each visit.

9.3.2 *Demographics and baseline characteristics*

Descriptive statistics for demographics, weight and height will be presented for all participants, by part.

9.3.3 *Medical/surgical history and prior/concomitant medication*

Medical/surgical history will be presented by part, system organ class (SOC) and preferred term (PT). Prior/concomitant medications will be presented by ATC level 4 and WHODrug Preferred name.

9.3.4 *Investigational medicinal product use*

Individual IMP use will be listed.

10 DATA DISPLAY PLAN

Tables and figures will only be generated if sufficient data, with sufficient variability exist to justify specific output being produced. Unscheduled/extra visits will generally not be presented in tables and summary figures but will be included in listings.

10.2 Trial tables

10.2.1 Demographic data

Table DM 1 Baseline characteristics and demographics – Part A (Full analysis set)

Assessment (unit)		[Redacted]					
Age (years)	n	x	x	x	x	x	x
	Mean (SD)	xx.x (xx.x)					
	Median (Min, Max)	xx.x (xx, xx)					
Height (cm)	n	x	x	x	x	x	x
	Mean (SD)	xxx.x (xx.x)					
	Median (Min, Max)	xxx.x (xxx, xxx)					
Weight (kg)	n	x	x	x	x	x	x
	Mean (SD)	xx.xx (xx.xx)					
	Median (Min, Max)	xx.xx (xx.x, xx.x)					
Body Mass Index (kg/m ²)	n	x	x	x	x	x	x
	Mean (SD)	xx.xx (xx.xx)					
	Median (Min, Max)	xx.xx (xx.x, xx.x)					
BSA (m ²)	n	x	x	x	x	x	x
	Mean (SD)	xx.xx (xx.xx)					
	Median (Min, Max)	xx.xx (xx.x, xx.x)					
Sex	Female	xx (xx%)					
	Male	xx (xx%)					
Ethnicity	Hispanic or latino	xx (xx%)					
	Not hispanic or latino	xx (xx%)					
	Not reported	xx (xx%)					

Assessment (unit)		[REDACTED]					
	Unknown	xx (xx%)	xx (xx%)	xx (xx%)	xx (xx%)	xx (xx%)	xx (xx%)
Race	American Indian or Alaska Native	xx (xx%)	xx (xx%)	xx (xx%)	xx (xx%)	xx (xx%)	xx (xx%)
	Asian	xx (xx%)	xx (xx%)	xx (xx%)	xx (xx%)	xx (xx%)	xx (xx%)
	Black or African American	xx (xx%)	xx (xx%)	xx (xx%)	xx (xx%)	xx (xx%)	xx (xx%)
	Native Hawaiian or Other Pacific Islander	xx (xx%)	xx (xx%)	xx (xx%)	xx (xx%)	xx (xx%)	xx (xx%)
	White	xx (xx%)	xx (xx%)	xx (xx%)	xx (xx%)	xx (xx%)	xx (xx%)

Data based on [ANALYSIS SET]. BSA: Body surface area. N: number of participants in treatment group. Percentages are based on the number of observations. n: Number of observations. SD: Standard deviation. SAS program: [PROGRAM NAME].sas.
Dataset version: ADXX YYYY-MM-DDTHH:MM:SS. Run by: [USERNAME] YYYY-MM-DDTHH:MM:SS. EDC data extracted: YYYY-MM-DDTHH:MM:SS.

Table DM 2 Baseline characteristics and demographics – [REDACTED]

[REDACTED]		[REDACTED]			
		x	x	x	x
Age (years)	n	x	x	x	x
	Mean (SD)	xx.x (xx.x)	xx.x (xx.x)	xx.x (xx.x)	xx.x (xx.x)
	Median (Min, Max)	xx.x (xx, xx)	xx.x (xx, xx)	xx.x (xx, xx)	xx.x (xx, xx)
Height (cm)	n	x	x	x	x
	Mean (SD)	xxx.x (xx.x)	xxx.x (xx.x)	xxx.x (xx.x)	xxx.x (xx.x)
	Median (Min, Max)	xxx.x (xxx, xxx)	xxx.x (xxx, xxx)	xxx.x (xxx, xxx)	xxx.x (xxx, xxx)
Weight (kg)	n	x	x	x	x
	Mean (SD)	xx.xx (xx.xx)	xx.xx (xx.xx)	xx.xx (xx.xx)	xx.xx (xx.xx)
	Median (Min, Max)	xx.xx (xx.x, xx.x)	xx.xx (xx.x, xx.x)	xx.xx (xx.x, xx.x)	xx.xx (xx.x, xx.x)
Body Mass Index (kg/m ²)	n	x	x	x	x
	Mean (SD)	xx.xx (xx.xx)	xx.xx (xx.xx)	xx.xx (xx.xx)	xx.xx (xx.xx)
	Median (Min, Max)	xx.xx (xx.x, xx.x)	xx.xx (xx.x, xx.x)	xx.xx (xx.x, xx.x)	xx.xx (xx.x, xx.x)

Assessment (unit)					
BSA (m2)	n	x	x	x	x
	Mean (SD)	xx.xx (xx.xx)	xx.xx (xx.xx)	xx.xx (xx.xx)	xx.xx (xx.xx)
	Median (Min, Max)	xx.xx (xx.x, xx.x)	xx.xx (xx.x, xx.x)	xx.xx (xx.x, xx.x)	xx.xx (xx.x, xx.x)
Sex	Female	xx (xx%)	xx (xx%)	xx (xx%)	xx (xx%)
	Male	xx (xx%)	xx (xx%)	xx (xx%)	xx (xx%)
Ethnicity	Hispanic or latino	xx (xx%)	xx (xx%)	xx (xx%)	xx (xx%)
	Not hispanic or latino	xx (xx%)	xx (xx%)	xx (xx%)	xx (xx%)
	Not reported	xx (xx%)	xx (xx%)	xx (xx%)	xx (xx%)
	Unknown	xx (xx%)	xx (xx%)	xx (xx%)	xx (xx%)
Race	American Indian or Alaska Native	xx (xx%)	xx (xx%)	xx (xx%)	xx (xx%)
	Asian	xx (xx%)	xx (xx%)	xx (xx%)	xx (xx%)
	Black or African American	xx (xx%)	xx (xx%)	xx (xx%)	xx (xx%)
	Native Hawaiian or Other Pacific Islander	xx (xx%)	xx (xx%)	xx (xx%)	xx (xx%)
	White	xx (xx%)	xx (xx%)	xx (xx%)	xx (xx%)

Data based on [ANALYSIS SET]. BSA: Body surface area. N: number of participants in treatment group. Percentages are based on the number of observations. n: Number of observations. SD: Standard deviation. SAS program: [PROGRAM NAME].sas.

Dataset version: ADXX YYYY-MM-DDTHH:MM:SS. Run by: [USERNAME] YYYY-MM-DDTHH:MM:SS. EDC data extracted: YYYY-MM-DDTHH:MM:SS.

Table DS 1 Participant disposition – Part A (All participants)

	Total (N=XXX)
Screened participants	xxx
Withdrawn prior to dose	xxx
Reason for withdrawal prior to dose	
--- Reason 1	xxx
--- Reason 2	xxx
--- ...	xxx
Participants included in trial	xxx
Allocated to arm	
	xxx
Withdrawn participants	
--- Reason 1	xxx
--- Reason 2	xxx
--- ...	xxx
Completed participants	xxx
Included in Full analysis set	xxx
Included in Pharmacokinetic analysis set	xxx
Participants at each visit	
--- Visit 1 - Screening	xxx
--- Visit 2 - Inpatient stay	xxx
--- Visit 3 - Follow-up	xxx

Data based on All participants. BSA: Body surface area. ¹The data for participants receiving placebo is presented pooled across groups. SAS program: [PROGRAM NAME].sas. Dataset version: ADXX YYYY-MM-DDTHH:MM:SS. Run by: [USERNAME] YYYY-MM-DDTHH:MM:SS. EDC data extracted: YYYY-MM-DDTHH:MM:SS.

Table DS 2 Participant disposition – Part B (All participants)

	Total (N=XXX)
Screened participants	XXX
Withdrawn prior to dose	XXX
Reason for withdrawal prior to dose	
--- Reason 1	XXX
--- Reason 2	XXX
--- ...	XXX
Participants included in trial	XXX
Allocated to arm	
	XXX
	XXX
	XXX
Withdrawn participants	
--- Reason 1	XXX
--- Reason 2	XXX
--- ...	XXX
Completed participants	XXX
Included in Full analysis set	XXX
Participants at each visit	
--- Visit 1 - Screening	XXX
--- Visit 2 – Treatment visit	XXX
--- Visit 3 - Follow-up	XXX

Data based on All participants. BSA: Body surface area. SAS program: [PROGRAM NAME].sas. Dataset version: ADXX YYYY-MM-DDTHH:MM:SS. Run by: [USERNAME] YYYY-MM-DDTHH:MM:SS. EDC data extracted: YYYY-MM-DDTHH:MM:SS.

Table MH 1 Medical history events by system organ class and preferred term – Part A (Full analysis set)

| System organ class
Preferred term | xx (xx%) | xx | m |
|--------------------------------------|----------|----|----------|----|----------|----|----------|----|----------|----|----------|----|----|
| Total | xx (xx%) | xx | xx |
| [SOC 1] | xx (xx%) | xx | xx |
| [SOC 1 PT 1] | xx (xx%) | xx | xx |
| [SOC 1 PT 2] | xx (xx%) | xx | xx |
| [SOC 1 PT ...] | xx (xx%) | xx | xx |
| [SOC 2] | xx (xx%) | xx | xx |
| [SOC 2 PT 1] | xx (xx%) | xx | xx |
| [SOC 2 PT 2] | xx (xx%) | xx | xx |
| [SOC 2 PT ...] | xx (xx%) | xx | xx |
| [SOC ...] | xx (xx%) | xx | xx |
| [SOC ... PT 1] | xx (xx%) | xx | xx |
| [SOC ... PT 2] | xx (xx%) | xx | xx |
| [SOC ... PT ...] | xx (xx%) | xx | xx |

Data based on [ANALYSIS SET]. BSA: Body surface area. N: number of participants in the treatment group. Percentages are based on N. n: number of participants. m: number of events. The following events are coded with multiple terms and are represented as separate events in tables and listings: '[MH TERM 1], [MH TERM 2]'. See listings for detailed information. SAS program: [PROGRAM NAME].sas.

Dataset version: ADXX YYYY-MM-DDTHH:MM:SS. Run by: [USERNAME] YYYY-MM-DDTHH:MM:SS. EDC data extracted: YYYY-MM-DDTHH:MM:SS.

Table MH 2 Medical history events by system organ class and preferred term – Part B (Full analysis set)

| System organ class
Preferred term | xx (xx%) | xx |
|--------------------------------------|----------|----|----------|----|----------|----|----------|----|
| Total | xx (xx%) | xx |

System organ class Preferred term									m
[SOC 1]	xx (xx%)	xx	xx						
[SOC 1 PT 1]	xx (xx%)	xx	xx (xx%)						
[SOC 1 PT 2]	xx (xx%)	xx	xx (xx%)						
[SOC 1 PT ...]	xx (xx%)	xx	xx (xx%)						
[SOC 2]	xx (xx%)	xx	xx (xx%)						
[SOC 2 PT 1]	xx (xx%)	xx	xx (xx%)						
[SOC 2 PT 2]	xx (xx%)	xx	xx (xx%)						
[SOC 2 PT ...]	xx (xx%)	xx	xx (xx%)						
[SOC ...]	xx (xx%)	xx	xx (xx%)						
[SOC ... PT 1]	xx (xx%)	xx	xx (xx%)						
[SOC ... PT 2]	xx (xx%)	xx	xx (xx%)						
[SOC ... PT ...]	xx (xx%)	xx	xx (xx%)						

Data based on [ANALYSIS SET]. BSA: Body surface area. N: number of participants in the treatment group. Percentages are based on N. n: number of participants. m: number of events. The following events are coded with multiple terms and are represented as separate events in tables and listings: '[MH TERM 1], [MH TERM 2]'. See listings for detailed information. SAS program: [PROGRAM NAME].sas.

Dataset version: ADXX YYYY-MM-DDTHH:MM:SS. Run by: [USERNAME] YYYY-MM-DDTHH:MM:SS. EDC data extracted: YYYY-MM-DDTHH:MM:SS.

Table CM 1 Prior medications by ATC level 4 and preferred name – Part A (Full analysis set)

ATC Name Level 4 Preferred Name									Total (N=XX)
	m	n (%)	m						
Total	xx (xx%)	xx	xx (xx%)	xx	xx (xx%)	xx	xx (xx%)	xx	xx (xx%)
[L4 1]	xx (xx%)	xx	xx (xx%)	xx	xx (xx%)	xx	xx (xx%)	xx	xx (xx%)
[L4 1 PN 1]	xx (xx%)	xx	xx (xx%)	xx	xx (xx%)	xx	xx (xx%)	xx	xx (xx%)

ATC Name Level 4 Preferred Name	[REDACTED]												Total (N=XX)
	n (%)	m											
[L4 1 PN 2]	xx (xx%)	xx	xx										
[L4 1 PN ...]	xx (xx%)	xx	xx										
[L4 2]	xx (xx%)	xx	xx										
[L4 2 PN 1]	xx (xx%)	xx	xx										
[L4 2 PN 2]	xx (xx%)	xx	xx										
[L4 2 PN ...]	xx (xx%)	xx	xx										
[L4 ...]	xx (xx%)	xx	xx										
[L4 ... PN 1]	xx (xx%)	xx	xx										
[L4 ... PN 2]	xx (xx%)	xx	xx										
[L4 ... PN ...]	xx (xx%)	xx	xx										

Data based on [ANALYSIS SET]. BSA: Body surface area. N: number of participants in the treatment group. Percentages are based on N. n: number of participants. m: number of events. The following records are coded with multiple terms and are represented as separate events in tables and listings: '[CM TERM 1], [CM TERM 2]'. See listings for detailed information. SAS program: [PROGRAM NAME].sas

Dataset version: ADXX YYYY-MM-DDTHH:MM:SS. Run by: [USERNAME] YYYY-MM-DDTHH:MM:SS. EDC data extracted: YYYY-MM-DDTHH:MM:SS.

Table CM 2 Prior medications by ATC level 4 and preferred name – Part B (Full analysis set)

ATC Name Level 4 Preferred Name	[REDACTED]							m
	xx (xx%)	xx	xx (xx%)	xx	xx (xx%)	xx	xx (xx%)	
Total	xx (xx%)	xx						
[L4 1]	xx (xx%)	xx						
[L4 1 PN 1]	xx (xx%)	xx						
[L4 1 PN 2]	xx (xx%)	xx						
[L4 1 PN ...]	xx (xx%)	xx						

ATC Name Level 4 Preferred Name									m
[L4 2]	xx (xx%)	xx	xx						
[L4 2 PN 1]	xx (xx%)	xx	xx (xx%)						
[L4 2 PN 2]	xx (xx%)	xx	xx (xx%)						
[L4 2 PN ...]	xx (xx%)	xx	xx (xx%)						
[L4 ...]	xx (xx%)	xx	xx (xx%)						
[L4 ... PN 1]	xx (xx%)	xx	xx (xx%)						
[L4 ... PN 2]	xx (xx%)	xx	xx (xx%)						
[L4 ... PN ...]	xx (xx%)	xx	xx (xx%)						

Data based on [ANALYSIS SET]. BSA: Body surface area. N: number of participants in the treatment group. Percentages are based on N. n: number of participants. m: number of events. The following records are coded with multiple terms and are represented as separate events in tables and listings: '[CM TERM 1], [CM TERM 2]'. See listings for detailed information. SAS program: [PROGRAM NAME].sas
Dataset version: ADXX YYYY-MM-DDTHH:MM:SS. Run by: [USERNAME] YYYY-MM-DDTHH:MM:SS. EDC data extracted: YYYY-MM-DDTHH:MM:SS.

Table CM 3 Concomitant medications by ATC level 4 and preferred name – Part A (Full analysis set)

ATC Name Level 4 Preferred Name											Total (N=XX)	
Total	xx (xx%)	xx	xx (xx%)	xx								
[L4 1]	xx (xx%)	xx	xx (xx%)	xx								
[L4 1 PN 1]	xx (xx%)	xx	xx (xx%)	xx								
[L4 1 PN 2]	xx (xx%)	xx	xx (xx%)	xx								
[L4 1 PN ...]	xx (xx%)	xx	xx (xx%)	xx								
[L4 2]	xx (xx%)	xx	xx (xx%)	xx								
[L4 2 PN 1]	xx (xx%)	xx	xx (xx%)	xx								

ATC Name Level 4 Preferred Name											Total (N=XX)
	m	n (%)	m								
[L4 2 PN 2]	xx (xx%)	xx	xx (xx%)	xx	xx (xx%)	xx	xx (xx%)	xx	xx (xx%)	xx	xx (xx%)
[L4 2 PN ...]	xx (xx%)	xx	xx (xx%)	xx	xx (xx%)	xx	xx (xx%)	xx	xx (xx%)	xx	xx (xx%)
[L4 ...]	xx (xx%)	xx	xx (xx%)	xx	xx (xx%)	xx	xx (xx%)	xx	xx (xx%)	xx	xx (xx%)
[L4 ... PN 1]	xx (xx%)	xx	xx (xx%)	xx	xx (xx%)	xx	xx (xx%)	xx	xx (xx%)	xx	xx (xx%)
[L4 ... PN 2]	xx (xx%)	xx	xx (xx%)	xx	xx (xx%)	xx	xx (xx%)	xx	xx (xx%)	xx	xx (xx%)
[L4 ... PN ...]	xx (xx%)	xx	xx (xx%)	xx	xx (xx%)	xx	xx (xx%)	xx	xx (xx%)	xx	xx (xx%)

Data based on [ANALYSIS SET]. BSA: Body surface area. N: number of participants in the treatment group. Percentages are based on N. n: number of participants. m: number of events. The following records are coded with multiple terms and are represented as separate events in tables and listings: '[CM TERM 1], [CM TERM 2]'. See listings for detailed information. SAS program: [PROGRAM NAME].sas.

Dataset version: ADXX YYYY-MM-DDTHH:MM:SS. Run by: [USERNAME] YYYY-MM-DDTHH:MM:SS. EDC data extracted: YYYY-MM-DDTHH:MM:SS.

Table CM 4 Concomitant medications by ATC level 4 and preferred name – Part B (Full analysis set)

ATC Name Level 4 Preferred Name									m
	xx (xx%)	xx							
Total	xx (xx%)	xx	xx						
[L4 1]	xx (xx%)	xx	xx						
[L4 1 PN 1]	xx (xx%)	xx	xx						
[L4 1 PN 2]	xx (xx%)	xx	xx						
[L4 1 PN ...]	xx (xx%)	xx	xx						
[L4 2]	xx (xx%)	xx	xx						
[L4 2 PN 1]	xx (xx%)	xx	xx						
[L4 2 PN 2]	xx (xx%)	xx	xx						
[L4 2 PN ...]	xx (xx%)	xx	xx						

ATC Name Level 4 Preferred Name									m
[L4 ...]	xx (xx%)	xx	xx						
[L4 ... PN 1]	xx (xx%)	xx	xx						
[L4 ... PN 2]	xx (xx%)	xx	xx						
[L4 ... PN ...]	xx (xx%)	xx	xx						

Data based on [ANALYSIS SET]. BSA: Body surface area. N: number of participants in the treatment group. Percentages are based on N. n: number of participants. m: number of events. The following records are coded with multiple terms and are represented as separate events in tables and listings: '[CM TERM 1], [CM TERM 2]'. See listings for detailed information. SAS program: [PROGRAM NAME].sas.

Dataset version: ADXX YYYY-MM-DDTHH:MM:SS. Run by: [USERNAME] YYYY-MM-DDTHH:MM:SS. EDC data extracted: YYYY-MM-DDTHH:MM:SS.

